6 TRIAL TREATMENTS

Trial treatment is defined as any investigational treatment intended to be administered to a trial subject according to the trial protocol. An “IMP” is any medicinal product which is

being tested or used as a reference in a clinical trial (the tested product and its reference products, including placebos). Concomitant therapy is not considered trial treatment.

6.1 Trial treatments administered

IMP name	BNT162b4	BNT162b2 Bivalent (WT/OMI BA.4/BA.5) referred to as "BNT162b2 Bivalent"	BNT162b2 Monovalent (OMI XBB.1.5)
Type	Investigational. Nucleoside-modified RNA vaccine which encodes non-spike protein antigens from SARS-CoV-2 (i.e., nucleocapsid protein, membrane protein CCI [REDACTED])	Investigational and active comparator. Nucleoside-modified RNA vaccine which encodes spike protein antigens from SARS-CoV-2. BNT162b2 Bivalent is supplied as a co-formulated drug product of BNT162b2 Wild Type and BNT162b2 OMICRON [B.1.1.529 sublineages BA.4/BA.5] in a single vial.	Investigational. Nucleoside-modified RNA vaccine which encodes spike protein antigen from SARS-CoV-2. BNT162b2 Monovalent (OMI XBB.1.5) is supplied in a single vial.
Dose levels	5 µg, 10 µg, 15 µg, 30 µg	30 µg (15 µg BNT162b2 + 15 µg BNT162b2 OMI BA.4/BA.5)	30 µg
Allocation to IMP	Trial subjects in Cohorts 1 to 4 who receive BNT162b4 in combination with a BNT162b2-based vaccine will be randomized using an online randomization tool. Trial subjects in single arm Cohort 5 who are assigned to receive BNT162b4 alone in an unblinded fashion without a control/placebo group.	Trial subjects will be randomized using an online randomization tool. Randomization 3:1 for all cohorts: to BNT162b4 + BNT162b2 Bivalent: BNT162b2 Bivalent.	Trial subjects will receive BNT162b2 Monovalent (XBB.1.5) in an unblinded fashion without a control/placebo group (non-randomized).
IMP administration	Intramuscular injection in the mid-deltoid muscle of the non-dominant arm. For "BNT162b4 + BNT162b2 Bivalent" administration, BNT162b4 plus BNT162b2 Bivalent will be co-administered as a single injection. BNT162b4 alone will be administered as a single injection. For details regarding IMP preparation for administration, see the Pharmacy Manual.	Intramuscular injection in the mid-deltoid muscle of the non-dominant arm. For administration, BNT162b4 plus BNT162b2 Monovalent (OMI XBB.1.5) will be co-administered as a single injection. For details regarding IMP preparation for co-administration, see the Pharmacy Manual.	Intramuscular injection in the mid-deltoid muscle of the non-dominant arm. For administration, BNT162b4 plus BNT162b2 Monovalent (OMI XBB.1.5) will be co-administered as a single injection. For details regarding IMP preparation for co-administration, see the Pharmacy Manual.
Vaccination schedules	IMP will be administered on Day 1 (Dose 1) and, for treatment groups administered BNT162b4 + BNT162b2 Bivalent, again 6 to 7 months after Day 1 (for Dose 2), or BNT162b4 + BNT162b2 Monovalent (OMI XBB.1.5) 6 to 7 months after Day 1 (for Dose 2), or BNT162b4 alone: 2 months after Day 1 (for Dose 2).		
Packaging and labeling	IMP will be provided in glass vials. Each vial will be labeled as per country requirements. For details of the IMP packaging, labeling, and IMP sourcing, see the Pharmacy Manual.		

Abbreviations: IMP = investigational medicinal product; OMI = Omicron CCI

SARS-CoV-2 = severe acute respiratory syndrome coronavirus 2; WT = Wild Type.

6.2 Preparation/handling/storage/accountability

The investigator or designee must confirm appropriate temperature conditions have been maintained during transit for all trial treatment received and any discrepancies are reported and resolved before use of the trial treatment.

Only trial subjects enrolled in the trial may receive trial treatment and only authorized site personnel may supply or administer trial treatment. All trial treatment must be stored in a secure, environmentally controlled, and monitored (manual or automated) area in accordance with the labeled storage conditions with access limited to authorized site personnel.

The investigator is accountable for trial treatment accountability, reconciliation, and record maintenance (i.e., receipt, reconciliation, and final disposition records).

Any non-compliance with the provided storage conditions should be reported to the sponsor upon discovery along with any actions taken. Once non-compliance is identified, the trial treatment must be quarantined and not used until the sponsor provides permission to use/discard/return the trial treatment.

Further guidance and information for the storage, handling, and final disposition of trial treatment will be provided in the Pharmacy Manual.

6.3 Measures to minimize bias: randomization and blinding

Cohorts 1, 2, 3a, 3b, 4a, and 4b are observer-blind for Dose 1, through Visit 5 only. Since only prior recipients of BNT162b4 will receive Dose 2, Dose 2 will be open-label. Trial subjects will be permitted to be unblinded from Visit 5.

Cohort 5 is single arm and open-label for Dose 1 and Dose 2.

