3 OBJECTIVES AND ENDPOINTS

Objectives, estimands and endpoints – Cohorts 1 to 4

OBJECTIVES	ESTIMAND *	ENDPOINTS
Primary objectives		
To describe the safety and tolerability of one and two doses of BNT162b4 + BNT162b2 Bivalent, one dose of BNT162b4 + BNT162b2 Monovalent (OMI XBB.1.5) as a booster, or one dose of BNT162b2 Bivalent alone at each applicable DL in healthy adults aged 18 years and older, with and without evidence of prior SARS-CoV-2 infection who previously received at least three prior doses of an authorized RNA-based COVID-19 vaccine.	For each DL cohort, the frequency of dosed subjects with: 
Solicited local reactions at the injection site recorded up to 7 d after every IMP dose.Solicited systemic events recorded up to 7 d after every IMP dose.Subjects with at least one AE occurring up to 28 d after every IMP dose.Subjects with at least one SAE occurring up to 6 months after every IMP dose.	
Solicited local reactions (pain, erythema / redness, induration / swelling)Solicited systemic events (vomiting, diarrhea, headache, fatigue, myalgia, arthralgia, chills and fever)AEsSAEs
	For each DL cohort, the percentage of dosed subjects with: 
Abnormal hematology or chemistry laboratory values 3 d (Dose 1 sentinel group only) and 7 d after every dose.Grading shifts in hematology or chemistry laboratory assessments between baseline and 3 d (Dose 1 sentinel group only) and 7 d after every IMP dose.	
Hematology and chemistry laboratory parameters (see Section 10.3)
	For each DL cohort, the percentage of dosed subjects with: 
New ECG abnormalities 3 d (Dose 1 sentinel group only) and 7 d after every IMP dose.	
ECG abnormalities consistent with probable or possible myocarditis or pericarditis as defined in the protocol
Secondary objectives		

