6.3.2 Blinding

For Cohorts 1 to 4, this is an observer-blind trial until Visit 5 (or later, if subjects only consent to Dose 2 later). Individuals will be unblinded as described in the SoA in Section 1.3. Further details relevant to blinding/unblinding procedures will be provided in the Blind Management Plan.

Cohort 5 is open-label.

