6.3.2.2 Blinding of trial site personnel

The trial staff dispensing and administering the vaccine will be unblinded, but all other trial personnel, including the principal investigator, will be blinded as described in the SoA in Section [1.3](#). The principal investigator will assign the responsibility of unblinded dispenser and unblinded administrator to persons who will not participate in the evaluation of any trial subject. More than one unblinded dispenser/administrator may be assigned. A member of the trial site personnel or clinic pharmacy should fulfill this role. Contact between the unblinded dispenser/administrator and trial subjects should be kept to a minimum.

The investigator, trial coordinator, and any site staff other than the unblinded dispenser/administrator must not be allowed to know the investigational product assigned to any trial subject and must not be allowed to see the investigational product containers.

BNT162b4 and BNT162b2 Bivalent do not differ in physical appearance but the trial treatments differ slightly in volume (and thus could lead to unblinding, e.g., when administering the IMP or recording the administered IMP volume), details of the trial treatment blinding measures will be provided in the Blind Management Plan.

The trial may be unblinded to site personnel at timepoints as decided by the sponsor.

6.3.2.2.1 *Unblinding of trial subjects*

In case of an emergency, the investigator has the sole responsibility for determining if unblinding of a trial subject's trial treatment assignment is warranted. Trial subject safety must always be the first consideration in making such a determination. Prior to the trial start, the investigator will be provided with guidance relevant to the emergency unblinding procedure.

If the investigator decides that unblinding is warranted to ensure the safety of a trial subject, the investigator should make every effort to contact the sponsor prior to unblinding the trial subject's trial treatment assignment unless this could delay further management of the trial subject.

If a subject's trial treatment assignment is unblinded, the sponsor must be notified within 24 h after breaking the blind. The date and reason that the blind was broken must be recorded in the source documentation and case report form (CRF).

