N-binding antibody test to detect prior SARS-CoV-2 infection	X m 5 mL														
Rapid antigen test for SARS-CoV-2 infection		X m													X
Oral swabs for NAAT-based SARS-CoV-2 testing and sequencing for	X	X			X	X	X	X	X t	X	X	X	X	X	X

Activity	Visit 0 (V0)														Early term. Visit	Unsche- duled 
		V1	V1	V2 o	V3	V4	V5	V6 p	V7 p	V8	V9	V10	V11			
Visit description	Screening at ≤28 d pre-V1	Pre-dose	Dose 1 (D1)	3 d post-D1	7 d post-D1	28 d post-D1	3 m FU post-D1	6 m FU post-D1	Dose 2 (6 to 7 m post-D1)	7 d post-D2	28 d post-D2	3 m FU post-D2	6 m FU post-D2			Potential COVID-19 Illness Visit
Days relative to Dose 1	N/A	1	1	3	8	29	90	180							N/A	N/A
Permitted visit window				+2 d	+2 d	±3 d	±7 d	-10 d to +30 d	+30 d post-V6	+2 d from 7 d post-D2	±3 d from 28 d post-D2	±7 d from 3 m post-D2	±10 d from 6 m post-D2			
surveillance (central test site)																
Oral swab for NAAT-based SARS-CoV-2 (local test site)	X u	X u														X
Allocate to trial treatment (Randomization)		X														
IMP administration			X						X r							
Unblind participants who proceed to Dose 2							X	X (if not done at V5)	X (if not done at V5)							
Investigator assessment of reactogenicity for up to 1 h after IMP administration			X						X s							
Issue thermometer/confirm participants still have thermometer		Issue							Confirm							

Activity	Visit 0 (V0)	V1	V1	V2 o	V3	V4	V5	V6 P	V7 P	V8	V9	V10	V11	Early term. Visit	Un sche- duled l
	Screening at ≤28 d pre-V1	Pre- dose	Dose 1 (D1)	3 d post- D1	7 d post- D1	28 d post- D1	3 m FU post- D1	6 m FU post-D1	Dose 2 (6 to 7 m post-D1)	7 d post-D2	28 d post-D2	3 m FU post-D2	6 m FU post-D2		Potential COVID-19 Illness Visit
Days relative to Dose 1	N/A	1	1	3	8	29	90	180						N/A	N/A
Permitted visit window				+2 d	+2 d	±3 d	±7 d	-10 d to +30 d	+30 d post-V6	+2 d from 7 d post-D2	±3 d from 28 d post-D2	±7 d from 3 m post-D2	±10 d from 6 m post-D2		
Blood draws for humoral response assessments h		X 20 mL			X 20 mL	X 20 mL	X 20 mL	X 20 mL	X s.t 20 mL	X 20 mL	X 20 mL	X 20 mL	X 20 mL	X 20 mL	
Issue, train, or collect subject e-diaries; remind participants i		Issue, train		Remind					Remind	Collect				Collect	

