- h. Leftover blood after completion of the assessments may be used for additional biomarker analyses and/or development of analytical methods.
- i. Trial site personnel will remind the participants to record the oral body temperature and the worst grade for each symptom in the e-diary at approximately the same time every evening on the day of IMP administration and then every day in the evening for a total of seven consecutive days. Ask/remind the subject to contact the site if they experience any severe or potentially life-threatening reactogenicity events. Trial site personnel will remind the participants to record the use of antipyretic/analgesic medication to treat symptoms associated with IMP administration for 7 d after each IMP dose using the e-diary.
- j. For FU visits, only adverse event(s) of special interest, any SAEs, and all AEs linked to confirmed COVID-19 cases will be recorded. SAEs must be recorded upon awareness.

- k. For FU visits, only any prohibited medication (including SARS-CoV-2 non-trial vaccinations) will be recorded.
- l. Optimally within 3 d after potential COVID-19 illness onset. All known NAAT-based SARS-CoV-2 positive participants, from randomization until end of trial, will be asked for an additional unscheduled visit to define the COVID-19 illness as per Section 8.2.8 of protocol. The COVID-19 illness visit will define the illness as either confirmed COVID-19, unconfirmed COVID-19, or confirmed severe COVID-19.
- m. The results must be available prior to administration of trial treatment at Visit 1. If the initial N-binding antibody test is negative, this test needs to be repeated if performed >28 d prior to the planned vaccination.
- n. Blood samples for **CCI** assessment at "Potential COVID-19 Illness Visit" should only be collected if the visit occurs more than 2 months after the last IMP dose.
- o. This visit will apply to sentinel participants only.
- p. Visit 6 and Visit 7 can (should ideally) occur on the same day.
- q. Informed consent can be obtained for Dose 2 at either Visit 5, 6 or Visit 7.
- r. Only for participants that received BNT162b2 Bivalent + BNT162b4 for Dose 1 and who consented to a second (Dose 2).
- s. To be completed before administration of Dose 2.
- t. The assessment/sampling at Visit 7 will only be performed if not done at Visit 6.
- u. Not for Cohorts 4a and 4b.

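### The blind may be broken at Visit 5 (Day 90) for participants proceeding to Dose 2, although Dose 2 comes only at Visit 6/7 and SAE follow-up after Dose 1 runs to 6 months

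*Protocol*

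**What the plan says.** The documents describe the end of the blind in Cohorts 1 to 4 in three ways.

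- Protocol 6.3 (repeated in SAP 1.2): "Cohorts 1, 2, 3a, 3b, 4a, and 4b are observer-blind for Dose 1, through Visit 5 only". It adds: "Trial subjects will be permitted to be unblinded from Visit 5". The context is that only BNT162b4 recipients can have Dose 2, which is open-label.
- Protocol 6.3.2 is looser: "this is an observer-blind trial until Visit 5 (or later, if subjects only consent to Dose 2 later". It refers to the schedule of activities for the detail.
- The schedule (SAP Appendix 4, Table 10) has a row headed "Unblind participants who proceed to Dose 2". It is marked at Visit 5, and again at Visits 6 and 7 for anyone not yet unblinded.

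On timing, Visit 5 is Day 90 and Visit 6 is Day 180. Dose 2 is at Visit 7, 6 to 7 months after Dose 1, and combining Visits 6 and 7 is preferred. Footnote q says: "Informed consent can be obtained for Dose 2 at either Visit 5, 6 or Visit 7".

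On endpoints, the primary estimand in Protocol 3 includes "Subjects with at least one SAE occurring up to 6 months after every IMP dose". Protocol 9.4.2 lists related SAEs, any AESI and related AESIs among the summaries, and SAP 6.5.1.3 summarises SAEs and AESIs to 6 months after each dose in Cohorts 1 to 4.

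**The concern.** The comparison of BNT162b4 plus Bivalent with Bivalent alone after Dose 1 is the only randomised comparison in the trial. The stated ground for breaking the blind concerns eligibility for Dose 2, which is not given for roughly another 90 days after Visit 5. Unblinding at Visit 5 therefore opens Months 3 to 6 of that comparison before Dose 2 calls for it.

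Two things are at stake. First, whether an SAE or AESI is related is an investigator judgement (Protocol 10.4.3), and it feeds the related-SAE and related-AESI rates. Under Protocol 7.1.1, only events in BNT162b4 recipients count toward a cohort pause, so an investigator who knows the arm also knows what a causality call can trigger. Secondly, the schedule row names only those going on to Dose 2, and controls cannot go on. Read literally, it unblinds one arm and leaves the other blinded, so late events could be reported and judged under different conditions in the two arms.

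**Working it through.** The plan gives no figure for the share of follow-up that is blinded, so there is none to reproduce. Protocol Table 6 (probability of seeing at least one AE) is not an input here.

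**Inputs**
- Dose 1: Day 1. Visit 5: Day 90, window ±7, so Days 83 to 97. Visit 6: Day 180, window −10 to +30, so Days 170 to 210 (schedule of activities).
- Planned numbers: 45 BNT162b4 and 15 control in each of six cohorts, so 270 and 90 (Protocol Table 2). The BNT162b4 share is 270/360 = 0.75.

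**Share of the Dose 1 window unblinded, for one person unblinded at Visit 5**

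Share = (end day − Visit 5 day) / (end day − 1).
- Nominal: (180 − 90)/(180 − 1) = 90/179 = 50.3%.
- Smallest, with a late Visit 5 and an early Visit 6: (170 − 97)/(170 − 1) = 73/169 = 43.2%.
- Largest, with an early Visit 5 and a late Visit 6: (210 − 83)/(210 − 1) = 127/209 = 60.8%.

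**Share pooled over both arms**

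Follow the schedule row literally, so that only BNT162b4 recipients are unblinded, and let u be the fraction of them unblinded at Visit 5. The pooled share is 0.75 × u × 0.503. The documents give no Dose 2 uptake, so u is an assumption.
- u = 100%: 37.7% (BNT162b4 arm 50.3%, control 0%).
- u = 75%: 28.3% (37.7% against 0%).
- u = 50%: 18.9% (25.1% against 0%).
- u = 25%: 9.4% (12.6% against 0%).

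Only if everyone in both arms is unblinded at Visit 5 does the pooled share reach 50.3%. The row does not list controls. A control who asks for Dose 2 at Visit 5 is ineligible under inclusion criterion 17, however, and a refusal would reveal the arm, so the true figure could lie above the literal reading.

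**Endpoints outside the exposed period**

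The 7-day visit falls by Day 8 + 2 = Day 10 and the 28-day visit by Day 29 + 3 = Day 32. Both precede the earliest Visit 5, Day 83. Post-Dose 1 solicited reactions, 28-day AEs, laboratory values, ECGs and Day 28 titers are therefore all observed before the blind can be broken under this rule.

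**If unblinding waits for Visit 6/7**

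With Visit 6 on Day 180 or later, the unblinded share of the 180-day window is 0%. With Visit 6 at its earliest, Day 170, it is (180 − 170)/(180 − 1) = 10/179 = 5.6%.

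**Who and when, side by side**

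Protocol 6.3 ends the blind for the cohorts at Visit 5 and permits unblinding of subjects in general. Protocol 6.3.2 lets the end move with Dose 2 consent. The schedule confines it to those proceeding to Dose 2, at Visit 5, 6 or 7. Protocol 7.1.2 attaches a treatment-discontinuation rule to unblinding before Visit 5. These do not describe one rule.

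**The case against.** The strongest reply is that unblinding at Visit 5 is permitted rather than required, may come later, and is listed only for those taking Dose 2. That stands, and it rules out reading the plan as unblinding half of all randomised follow-up. A reader might infer that figure from the Visit 5 wording, but it needs both arms unblinded at Day 90.

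It can also be said that the reach is narrow. The primary SAE estimand counts any SAE regardless of causality, seriousness rests largely on outcomes, AESIs are not in the primary estimand, and no hypothesis is tested. This limits the point to late SAEs and AESIs but does not remove it: related-event rates are planned summaries, and in a descriptive safety comparison no later step corrects uneven ascertainment.

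Three further readings are tempting and go too far.
- That the unblinding serves no purpose. The documents do give a reason to unblind, namely Dose 2 eligibility; what they lack is a reason for Day 90.
- That controls who learn their arm will leave and SAE follow-up will be lost unequally. This is conceivable, but the documents contain no dropout or uptake figure from which to size it, and the schedule row does not list controls for unblinding.
- That the sponsor can open the blind to sites without limit, from "The trial may be unblinded to site personnel at timepoints as decided by the sponsor" in Protocol 6.3.2.2. Protocol 6.3.2 places further procedures in the Blind Management Plan, which is not available here and may set limits.

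**Conclusion.** The point holds in a limited form. The plan lets the blind end at Day 90 for participants going on to Dose 2, gives no reason for that date, and already contains a later option that serves the same purpose. For each person unblinded at Visit 5, about half of the Dose 1 SAE/AESI window (43% to 61%) is unblinded. Pooled over the arms the share is at most about 38% under the schedule row as written, less with partial uptake at Visit 5, and 50% only in the extreme case.

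The imbalance between arms matters more than the total, because it can shift reporting and causality of late SAEs and AESIs in one arm only. No direction or size of bias can be derived from the documents.

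The conclusion assumes nominal visit days unless a range is given, planned enrolment, and that the investigator learns the arm when the participant does. Protocol 6.3.2.2 ties site blinding to the same schedule but does not say this outright. The separate finding, that Protocol 6.3, 6.3.2, 7.1.2 and the schedule need reconciling, rests on none of these assumptions.

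**What to change.** In Protocol 6.3 and 6.3.2 and in the schedule row (with SAP 1.2 and Appendix 4 to match), remove the Visit 5 unblinding option. Unblind only at Visit 6/7, once the Visit 6 AE/SAE assessment and blood sampling are complete and immediately before Dose 2. Take Dose 2 consent at Visit 6 or 7, which footnote q already allows. Emergency unblinding stays as it is.

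Consent should not be moved to a blinded, conditional step at Visit 5. Several restrictions in Protocol 5.1.1 start at Dose 2 consent and would then fall on controls who cannot receive Dose 2.

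At the same time, state in one place who is unblinded and when, and bring the four passages into line with it. The Protocol 7.1.2 rule keyed to Visit 5 has to be reconciled with whatever unblinding point is chosen; how that rule should read is for the sponsor.

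The cost is mainly wording in both documents. There is less lead time to plan Dose 2 visits and supply, which the unblinded staff would handle, and some controls learn only at Visit 6 that they are not eligible for Dose 2.

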6.3.1 Allocation of IMP

Treatment allocation will be done using an online randomization tool for Cohorts 1 to 4, and online open-label kit allocation will be used for Cohort 5.

Randomization for enrollment in Cohorts 1, 2, and 3a will be stratified based on N-binding antibody status and CCI

Randomization for enrollment in Cohort 3b will be stratified based on age and N-binding antibody status. Randomization for enrollment in Cohort 4b will be stratified based on age only. All subjects enrolled in Cohorts 4a and 4b, and all subjects giving consent for Dose 2 will be eligible CCI

For Cohorts 3b and 4b, the age group distribution enrolled will be ~60% of subjects aged ≥ 65 yrs and ~40% of subjects aged >55 to <65 yrs.

All subjects in Cohort 5 will be allocated to a single arm.

6.3.2 Blinding

For Cohorts 1 to 4, this is an observer-blind trial until Visit 5 (or later, if subjects only consent to Dose 2 later). Individuals will be unblinded as described in the SoA in Section 1.3. Further details relevant to blinding/unblinding procedures will be provided in the Blind Management Plan.

Cohort 5 is open-label.

